2.2 End-of-life care

A patient is considered in end-of-life care in case of a confirmatory negative response of the healthcare professional to the question “Would you be surprised if this patient died in the next 6-12 months?”, which is an accurate and widely used trigger for referring a patient to specialist palliative care.^{1,2}

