3. BACKGROUND

Deprescribing (i.e., discontinuing medication) is an important part of palliative care to prevent polypharmacy, which is associated with increased risk of adverse drug events, drug-drug and drug-disease interactions, reduced functional capacity, multiple geriatric syndromes, medication nonadherence, and higher healthcare costs. One of the most widely used cardiovascular drug classes in cancer patients in a palliative setting are antithrombotics, including anticoagulant and anti-platelet agents. Antithrombotic drugs, e.g., (DOACs), low-molecular-weight heparins (LMWH), vitamin-K antagonists (VKA) and so-called antiplatelet agents (such as acetyl salicylic acid and P2Y12 inhibitors), are indicated in patients with prosthetic heart valves, in those with venous thromboembolism (VTE), for stroke prevention in atrial fibrillation as well as in patients with established atherosclerotic cardiovascular disease (such as myocardial infarction, stroke, or peripheral artery disease). Most patients have been receiving these drugs chronically before their cancer was diagnosed, whilst others are being prescribed them in order to treat or prevent cancer-associated thrombosis. Obviously, decisions on deprescribing antithrombotics heavily depend on the indication of the antithrombotic drug in addition to patient and healthcare professional preferences and experience, and on the estimated life expectancy of the patient.

Understanding current patterns of management of antithrombotic therapy (ATT) as well as the rationale and preferences behind these patterns is crucial for improving clinical practice. Since deprescribing patterns and rationale may largely differ across countries, relevant data at a large scale is needed to fully understand and appreciate the relevant decision processes.

The insights gained in this study are a first step towards the development of a clinical decision tool supporting decisions on ATT in cancer patients.

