4. STUDY OBJECTIVE(S)

- >To explore and describe current European practice patterns with regard to the use of ATT in end-of-life care of cancer patients following 'flash mob research (FMR)' methodology.
- To evaluate and understand the processes and factors that inform decisions concerning the deprescription of ATT in the last year of life of cancer patients receiving ATT via a discrete choice experiment (DCE) among healthcare professionals, who deal with end-of-life care in cancer patients, or prescribe such medication to cancer patients.

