11. REGULATORY AND LEGAL REQUIREMENTS

As confirmed by the responsible ethics committee, due to the non-interventional nature of this study and since no personal data of patients will be recorded or processed, professional advice and/or submission of this protocol to the ethics committee before commencement of the survey is not required.

Data privacy of participating healthcare professionals will be taken into account in accordance with the European General Data Protection Regulation (GDPR). With the exception of the e-mail addresses of survey participants for the purpose of forwarding the survey link and information on survey launch and completion, no personal data will be stored or processed. As detailed in the information for prospective participants, participants implicitly consent to the use of their e-mail addresses for said purposes by pre-registering.

Data on patients will be sufficiently coarsened such that no identification will be possible. As an additional security measure, this part of the survey will be exported and analyzed separately from the other two sections (s. section 9 above).

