15.2 Survey: General questions

1. When do you consider a patient in end-of-life care? If the life expectancy is:
A. < 1 year B. < 6 months C. < 3 months D. < 2 weeks
2. When a patient is considered to be in end-of-life care, I **XXX** prescribe antithrombotic medication upon the diagnosis of a thrombotic complication.
A. never B. sometimes C. often D. always
3. Have you ever deprescribed (i.e., terminated) antithrombotic medication in end-of-life care of cancer patients?
A. no B yes

In case of no, the participant will not be redirected to certain questions.

4. When a patient is considered to be in end-of-life care, I **XXX** deprescribe antithrombotic medication.
A. never B. sometimes C. often D. always
5. Give an estimate of the frequency per year that you consider deprescribing antithrombotic medication in patients, considered to be in end-of-life care:
XXX /year
6. Give an estimate of the frequency per year that you actually deprescribed antithrombotic medication in patients considered to be in end-of-life care:

XXX /year

7. Do you discuss deprescription of antithrombotic medication in patients at the end of life with colleagues?
A. never B. sometimes C. frequently D. always
8. Please indicate what factors determine whether you prescribe antithrombotic medication in patients considered to be in end-of-life care.
9. Please indicate what factors determine whether you deprescribe antithrombotic medication in patients considered to be in end-of-life care.

15.2.1 Examples of factors relevant to questions 8 and 9

1. Antithrombotic medication:
 - DOAC or VKA
 - LMWH (therapeutic)
 - Antiplatelet agent
2. Indication for antithrombotic medication:
 - Atrial fibrillation
 - Treatment of acute VTE event or prevention of (recurrent) VTE
 - Mechanical heart valves
 - Other indication
3. Bleeding risk:
 - Low
 - High
4. Thrombotic risk:
 - Low
 - High
5. Sex:
 - Female
 - Male
 - Other
6. Age:
 - < 40 years
 - 40-75 years
 - > 75 years
7. Patient's performance status:
 - Eastern Clinical Oncology Group performance status (ECOG-PS) grade 0-2
[Oken MM et al. Am J Clin Oncol. 1982]
 - ECOG-PS grade ≥ 3
8. Patient prognosis:
 - < 6 months
 - < 3 months
 - < 2 weeks

9. Patient preference:

- Stop antithrombotic treatment
- Continue antithrombotic treatment

10. Other

Free text

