15.4 Survey: Questions on actual case decisions

In the following (multiple choice) questions, you will be asked to describe one to three actual cases of patients with active cancer, who were considered to receive end-of-life care, in which you considered deprescription of antithrombotic medication.

1. Please select the age category of the patient (*< 40 years; 40-75 years; 75 years or older*)
2. Please indicate the type of antithrombotic medication involved (*DOAC; VKA; LMWH (therapeutic); antiplatelet agent*)
3. Please select the indication of the antithrombotic medication (*atrial fibrillation; treatment of acute VTE-event, prevention of (recurrent) VTE; mechanical heart valves; other indication (free text)*)
4. Please indicate the patient's performance status (*ECOG-PS grade 0-2, ECOG-PS ≥ 3*)
5. Please indicate the estimated prognosis of the patient at the time of consideration (*< 6 months; < 3 months; < 2 weeks*)
6. Please specify the setting of the patient at the time of consideration (*at home without palliative care; at home with palliative care; at rehabilitation facility; at nursing facility; at hospice facility; in 'acute care' setting; other (free text)*).
7. Please select one or more of the attributes that played a role in your consideration of deprescribing the antithrombotic medication; multiple answers are possible (*type of antithrombotic medication; indication of the antithrombotic medication; bleeding risk; thrombotic risk; sex; age; patient's performance status; patient's preference; other (free text)*).
8. Did you decide to deprescribe the antithrombotic treatment? (*yes; no*)

9. If no:

Which of the following attributes made you decide not to deprescribe the antithrombotic drugs? Multiple choices are possible.

Experience with deprescribing: not enough; enough

Symptom burden: high

Burden of medication (administration): low

Thrombotic risk: high

Bleeding risk: low

Antithrombotic medication indication: atrial fibrillation; acute VTE-event, prevention of (recurrent) VTE; mechanical heart valves; other indication (free text)

Sex: male; female, other (selection to be made)

Age: (< 40 years; 40-64 years; 65-74 years; 75 years or older)

Patient's performance status: ECOG-PS 0-2

Patient's prognosis: < 2 weeks; < 3 months; < 6 months (selection to be made)

Patient's preference: continue antithrombotic treatment

Other (free text)

10. If yes:

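### 15.4 Q5 has no answer for a prognosis of 6 months or more, and 15.1 Q1 has no country code for participants from outside the eight listed countries, although the plan admits both groups

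*Combined protocol and SAP*

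**What the plan says.** **Prognosis.** Section 2.2 counts a patient as in end-of-life care when the clinician answers no to "Would you be surprised if this patient died in the next 6-12 months". In the general part of the survey, 15.2 Q1 asks below what life expectancy the respondent regards a patient as in end-of-life care, and offers "A. < 1 year B. < 6 months C. < 3 months D. < 2 weeks".

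For every actual case, 15.4 Q5 asks: "Please indicate the estimated prognosis of the patient at the time of consideration (*< 6 months; < 3 months; < 2 weeks". The list ends there. It has no free-text field, although 15.4 Q3 and Q6 each have one. Prognosis returns among the reasons for not deprescribing (Q9) and for deprescribing (Q10), both times as "Patient's prognosis: < 2 weeks; < 3 months; < 6 months (selection to be made". The list of considerations in 15.4 Q7, which ends "bleeding risk; thrombotic risk; sex; age; patient's performance status; patient's preference; other (free text", leaves prognosis out.

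**Country.** Section 7 names eight consortium countries and expects some participants from elsewhere. It makes a separate evaluation depend on how many, or what share, come from outside Europe. Section 8 sets a target of at least 800 professionals: 100 from each of the eight, or matching numbers from further countries. Section 10 has the country of practice checked at pre-registration. The only item that records it, 15.1 Q1, offers the eight countries and nothing else.

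**The concern.** The main analysis of the flash mob part is descriptive (Section 13), so the answer categories decide what can be reported. Section 3 names several drivers of a deprescribing decision, the last being "and on the estimated life expectancy of the patient". Any description of the case decisions by life expectancy would rest on Q5.

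If an admitted case has no true answer, the respondent must skip the item or pick a false category. The analyst then cannot tell a true '< 6 months' from a forced one. Repair afterwards would be difficult, because data collection lasts seven days and the patient data are anonymised and coarsened.

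For country, a participant from elsewhere might leave the item blank, choose a wrong country or not register. A wrong choice would also contaminate the results for the country chosen. The condition in Section 7 could not be evaluated from the only item that records country.

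**Working it through.** No sample size or power figure is involved. The check compares the answer lists with the plan's own scope.

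**1. Are cases of 6 months or more admitted?** The horizon in 2.2 runs to 12 months. A clinician can expect a patient to live, say, 9 months and still answer no to the surprise question. 15.2 Q1 also offers '< 1 year' as a threshold for end-of-life care. Neither source requires a prognosis of 6 months or more, but both allow it. A negative answer to the surprise question does not cap the estimate at 12 months either.

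**2. How many Q5 options are true for a given prognosis?** An option is true when the estimate lies below its bound (6 months, 3 months or 2 weeks).

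| Estimated prognosis | True options as written | True options with exclusive bands and an open top |
|---|---|---|
| < 2 weeks | 3 | 1 |
| 2 weeks to < 3 months | 2 | 1 |
| 3 to < 6 months | 1 | 1 |
| 6 months or more | 0 | 1 |

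The rows differ in weight. The rows with 3 and 2 true options show the nesting. If every respondent chose the narrowest true option, the answers could be recoded exactly as < 2 weeks, 2 weeks to < 3 months, and 3 to < 6 months. The row with 0 is a real gap, and no convention for choosing among the options repairs it.

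**3. Does another item recover the prognosis?** 15.4 Q7 does not list it. Q9 and Q10 record it only when it is given as a reason, and with the same three options. Their free-text line is for other reasons. Q5 is the only item that asks every case for prognosis.

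**4. Country.** Section 7 expects participants from further countries and Section 8 counts them. The list in 15.1 Q1 has 8 codes, and 0 of them fit such a participant. Section 11 limits the use of e-mail addresses to sending the link and study information, so these are no planned substitute.

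**5. Scale.** The Section 8 figures reproduce: 8 × 100 = 800 professionals, and 800 × 3 = 2400 cases. The documents do not say what share of cases has a prognosis of 6 months or more. As an assumption only, take 5% to 30%:

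- One case from each of 800 participants: 0.05 × 800 = 40, to 0.30 × 800 = 240 cases without a true answer.
- Three cases each: 0.05 × 2400 = 120, to 0.30 × 2400 = 720 cases.

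Even 800 cases is not a guaranteed minimum, because 15.4 takes only cases in which deprescription was considered.

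**6. Age 75 (minor).** In 15.4 Q1, age 75 falls both in 40-75 and in 75 or older. In 15.2.1 item 6 it falls in 40-75 only, and in Q9 and Q10 in 75 or older only. With an upper bound of 74, the bands of Q9 and Q10 collapse exactly: 40-64 plus 65-74 gives 40-74.

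**The case against.** The strongest case on the other side has four parts.

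- **No named analysis uses prognosis.** Section 13 mentions no such breakdown. The example scenarios in 15.3 vary performance status, thrombotic risk, bleeding risk and drug, but not prognosis. This stands, and it limits the consequence to description of the actual cases.
- **Respondents will choose the narrowest option.** Many may, and a one-line instruction would settle it. This stands for the nesting, which is therefore the milder defect. It does not help a case of 6 months or more.
- **The appendix may not be the final form.** Section 10 lists patient sex among the data collected, but 15.4 asks for it only within the reasons lists, so the two are not fully aligned. The final eCRF is not in the documents and should be checked. However, only 15.2.1 and 15.3 are headed as examples; 15.1 and 15.4 are presented as the survey questions.
- **Section 10 already plans to check country.** It does, so the intention is there. The answer list does not carry it out.

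A reader might infer four stronger points that the documents do not support:

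- *Section 4 fixes a one-year scope for Q5.* The wording "the deprescription of ATT in the last year of life of cancer patients receiving ATT" belongs to the second objective, which is tied to the discrete choice experiment. The first objective, on practice patterns, speaks only of end-of-life care. The case for the gap rests on 2.2 and 15.2 Q1.
- *The respondent's own threshold in 15.2 Q1 can never be linked to the case.* Section 11 says that "this part of the survey will be exported and analyzed separately from the other two sections". That describes separate export and analysis; it does not say that linkage is impossible. The threshold would in any event not be the prognosis of the individual case.
- *Three of the four prognosis ranges are equally defective.* That count gives the nesting the same weight as the gap.
- *The total of 800 is certainly safe, or certainly at risk.* Someone whose country is not listed might choose another or not register. The documents do not settle which.

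**Conclusion.** The point holds. As written, 15.4 Q5 and the prognosis lines of Q9 and Q10 have no category for an estimate of 6 months or more, although 2.2 and 15.2 Q1 admit such cases. Below that bound, '< 6 months' and '< 3 months' are ambiguous because no instruction says which true option to choose. Participants from further countries, whom Sections 7 and 8 expect and count, cannot be identified from the only country item.

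The size is unknown, and the counts above are arithmetic on an assumed share. Estimation of the discrete choice preferences does not use Q5. The named provisions affected are the conditional separate evaluation in Section 7 and the count of further countries in Section 8. The conclusion assumes that the eCRF follows the appendix. It should be fixed before launch, because the correction is cheap and the lost information would be hard to recover.

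**What to change.** Check the final eCRF first. If it follows the appendix, make these edits before data entry opens, with the country list changed before pre-registration where possible:

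- **15.4 Q5:** use exclusive bands: < 2 weeks; 2 weeks to < 3 months; 3 to < 6 months; 6 months or more; unknown/not estimated. The top band should be open, because a band closed at 12 months would leave longer estimates without a code.
- **15.4 Q9 and Q10, and example list 15.2.1 item 8:** use the same bands without 'unknown', so that stated reasons can be matched to Q5.
- **15.1 Q1:** add 'other European country (specify)' and 'country outside Europe (specify)'.
- **Minor, 15.4 Q1 and 15.2.1 item 6:** use 40-74 and 75 or older, so that age 75 has one category and agrees with Q9 and Q10.

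The cost is slightly longer lists: Q5 goes from three options to five, the other prognosis lists from three to four, and the country list from eight to ten. No question is added and no recruitment target changes.

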Which of the following attributes made you decide to deprescribe the antithrombotic drugs?

Multiple choices are possible.

Experience with deprescribing: enough

Symptom burden: low

Burden of medication (administration): high

Thrombotic risk: low

Bleeding risk: high

Antithrombotic medication indication: atrial fibrillation; acute VTE-event, prevention of (recurrent) VTE; mechanical heart valves; other indication (free text)

Sex: male; female, other (selection to be made)

Age: (< 40 years; 40-64 years; 65-74 years; 75 years or older)

Patient's performance status: ECOG-PS grade ≥ 3

Patient's prognosis: < 2 weeks; < 3 months; < 6 months (selection to be made)

Patient's preference: stop antithrombotic treatment

Other (free text)

Tumour-specific

11. Please select the type of cancer (*breast; lung; upper gastro-intestinal (GI); lower GI; endocrine; genito-urinary tract; brain; haematological; skin (excluding squamous/basal cell carcinoma); combination (select more than one); other (free text)*)
12. Please select the stage of cancer (*localized; regional; distant metastasis; not applicable*)
13. Please select the cancer treatment at the time of consideration/decision – multiple options possible (*none; surgery (in the previous 3 months); radiation therapy (in the previous month); chemotherapy (in the previous month); immunotherapy (in the previous month)*)
14. Please select the line of cancer treatment (*first-line, second-line, third-line, fourth-line, not applicable*)

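### In section 15.4, the factors offered as tick-boxes for considering deprescribing (question 7) differ from those for the decision (questions 9 and 10), so recorded reasons partly reflect the form

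*Combined protocol and SAP*

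**What the plan says.** Section 15.4 takes each respondent through one to three real cases. Question 7 is a multiple-response item: "Please select one or more of the attributes that played a role in your consideration of deprescribing the antithrombotic medication; multiple answers are possible". Its options begin with "type of antithrombotic medication; indication of the antithrombotic medication; bleeding risk" and the full list ends "bleeding risk; thrombotic risk; sex; age; patient's performance status; patient's preference; other (free text". Prognosis is not among them.

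Question 8 asks whether the drug was stopped. Respondents who answer no go to question 9, and those who answer yes go to question 10. Each asks which attributes led to that decision. Both offer prognosis, as "Patient's prognosis: < 2 weeks; < 3 months; < 6 months (selection to be made", and both offer experience with deprescribing, symptom burden and medication burden. The last appears as "Burden of medication (administration): low" in question 9 and as "Burden of medication (administration): high" in question 10. Neither offers the type of antithrombotic drug; the only drug-related option is its indication.

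Three other places bear on this:
- Section 3 names what deprescribing decisions rest on: the indication, patient and professional preferences and experience, "and on the estimated life expectancy of the patient".
- Question 5 of section 15.4 records the patient's prognosis as it stood when deprescribing was being considered.
- Section 15.2.1, the example list for the general questions, contains both drug type and "Patient prognosis".

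No section explains why the lists differ or says how free-text answers will be coded.

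**The concern.** Questions 7, 9 and 10 are the only items that ask for stated reasons in real cases. Under section 13 the survey results will be described with 95% confidence intervals. A reader of those tables will naturally set consideration beside decision. If prognosis is named seldom at consideration and often at decision, or drug type the other way round, that will look like a finding about how clinicians reason. Some of it will come from whether a box was offered.

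Section 3 presents the study as a first step towards a decision tool and treats the rationale behind practice as essential to understand, so under-recorded reasons matter. Sections 10 and 12 plan a single seven-day collection. A reason that was not prompted then cannot be recovered later.

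**Working it through.** The plan gives no figure on this point to reproduce. The check is a comparison of the lists, followed by an illustration on assumed values.

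**Step 1: the lists side by side** (excluding the free-text option, which all of them have).

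| Factor | Question 7 | Questions 9 and 10 | 15.2.1 (examples) |
|---|---|---|---|
| Indication | yes | yes | yes |
| Bleeding risk | yes | yes | yes |
| Thrombotic risk | yes | yes | yes |
| Sex | yes | yes | yes |
| Age | yes | yes | yes |
| Performance status | yes | yes | yes |
| Patient preference | yes | yes | yes |
| Drug type | yes | **no** | yes |
| Prognosis | **no** | yes | yes |
| Experience with deprescribing | **no** | yes | no |
| Symptom burden | **no** | yes | no |
| Medication burden | **no** | yes | no |

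Question 7 names 8 factors, questions 9 and 10 name 11, and 7 are shared. The union is 8 + 11 − 7 = 12, so 12 − 7 = 5 factors are prompted at one step only: four at the decision and one at consideration.

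**Step 2: could the omissions be deliberate?** For prognosis and experience, the documents point the other way. Section 3 names both life expectancy and experience among the things these decisions rest on, and question 5 ties prognosis to the moment of consideration. So prognosis cannot be set aside as relevant only at the decision. For drug type, question 7 accepts it as a possible reason for considering a stop, and no reason is given for not offering it as a reason for the decision.

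**Step 3: how the form could move the frequencies.** Let *p* be the share of cases in which a factor truly played a part, and *f* the probability that a respondent types it in when no box is offered. Assume for simplicity that a box would capture all of *p*. Then

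recorded share = *p* × *f*, and shortfall = *p* × (1 − *f*).

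Neither *p* nor *f* is in the documents. The values below are assumptions, with *f* from 5% to 50%.

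| Assumed *p* | Recorded share | Shortfall |
|---|---|---|
| 30% | 1.5% to 15% | 28.5 to 15 points |
| 50% | 2.5% to 25% | 47.5 to 25 points |
| 70% | 3.5% to 35% | 66.5 to 35 points |

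With *f* = 100% there is no shortfall.

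**Step 4: would the confidence interval show it?** The half-width is 1.96 × √(x(1 − x)/n), where x is the recorded share. With n = 2400, the planned maximum (800 respondents × 3 cases), it is about 0.5 points at x = 1.5% and 1.9 points at x = 35%. With n = 800 (one case each) it is about 0.8 and 3.3 points. These figures ignore clustering of cases within respondents. The interval measures sampling error and does not cover a shortfall caused by the form, and a larger sample does not remove that shortfall.

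**The case against.** Several objections carry weight.

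- **The lists are not closed.** All end in free text, so a reader who infers that the omitted factors will be recorded close to 0% goes beyond the documents. In the illustration above the recorded share reaches 35%, and nothing in the plan fixes the rate of free-text entry. This stands.
- **No ranking of case-level factors is planned.** A reader might infer that the study's ranking of factors is distorted. Section 13 makes this part descriptive and takes relative importance only from the DCE preference weights, which these boxes do not touch. Section 4 likewise assigns the factors behind decisions to the DCE. This stands, and confines the point to selection frequencies.
- **Comparison across survey sections is not planned.** Section 11 has the case section exported and analysed apart from the other two, so lost comparability with the general questions or the DCE is not a failure of a stated analysis. Section 15.2.1 is also headed as examples, and its gaps cannot be counted as defects of the final form. This stands too. But questions 7, 9 and 10 sit within the same section, so the contrast between them is unaffected by the separate export.
- **Little information is lost.** Question 2 records drug type and question 5 records prognosis, so both can be tabulated against question 8. Prognosis is also prompted once per case, at the decision. This is true, but an association with the decision is not a stated reason. Experience, symptom burden and medication burden are not recorded as case characteristics at all.
- **The questions differ in kind.** Question 7 asks what was weighed. Questions 9 and 10 ask what decided, mostly with the level fixed in advance; question 9, for example, offers bleeding risk only as low. Real differences between the two steps may exist, and matching factor names will not make the items fully like-for-like. This limits what the fix achieves, but it does not justify leaving a factor out of one list.

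**Conclusion.** The point holds as a questionnaire inconsistency within section 15.4 that should be corrected before launch. Five of 12 named factors are prompted at only one of the two steps: prognosis, experience, symptom burden and medication burden only at the decision, and drug type only at consideration. Their selection frequencies, and any contrast between question 7 and questions 9 and 10 for them, will partly reflect the form.

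The only assumption needed is that a listed box and an unprompted entry are not equally likely to be recorded. The size of the effect cannot be derived from the documents, and the figures in the working only illustrate it. The seven shared factors do not have this omission, and the DCE results are not affected.

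**What to change.** Before launch:
- Add prognosis, experience with deprescribing, symptom burden and medication burden to question 7.
- Add type of antithrombotic medication to questions 9 and 10.
- Optionally, align the example list in 15.2.1 by adding the three factors it lacks (experience, symptom burden, medication burden).

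If the form is already fixed, limit any comparison of question 7 with questions 9 and 10 to the seven shared factors, and report as a limitation that the other five were prompted at one step only.

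The cost is a few extra tick-boxes in the eCRF and a few seconds per case. The fallback costs nothing in data collection but gives up the comparison for five factors.
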